6.1.1.4 DURATION OF EXPOSURE

The maximal exposure to BQ 2.0 stimulation during a treatment session is 40 consecutive minutes.

6.1.1.5 FREQUENCY OF EXPOSURE

The BQ 2.0 will be used 5 times a week to a total of 45 treatment sessions in each subject.

6.1.1.6 SUMMARY/REPORT OF TEST VALIDATION STUDIES

For summary of test validation studies please refer to the IFU.

6.1.2 DOSING AND ADMINISTRATION

Randomized patients will receive active or sham study intervention sessions using BQ 2.0 (active or sham therapy, respectively), starting 4-21 days after stroke onset and no later than 2 days after randomization. Sessions will be conducted 5 times a week. Each session will last up to 60 minutes, with active or sham field being turned on for up to 40 minutes. The only difference between the BQ 2.0 active stimulation and sham therapy is that the sham device does not generate electromagnetic fields during treatment. Subjects in both the active intervention group

	The efficacy of a frequency-tuned electromagnetic field treatment in facilitating the recovery of subacute ischemic stroke patients – a pivotal study		
	No. BQ5	Ver. 4	Page 52 of 150

(BQ 2.0 group) and sham group will be asked to perform trial-specified physical and occupational therapy activities during each session, in addition to their standard care rehabilitation therapies.

During the study, 45 sessions of active or sham therapy will be conducted in either inpatient, outpatient or home setting.

. A trained member of the site study team (the “**Clinic Operator**”) will be responsible for training and approving the subject’s caregiver to operate the session independently.

Before an approval to operate a session independently (the “**Approval**”) is granted by the Clinic Operator, a Clinic Operator will train the caregiver and supervise the sessions, either in-person or remotely. Once an Approval was granted, sessions will be conducted with the assistance of a caregiver while the Clinic Operator will provide periodic oversight (combined audio and video remote conferencing or audio only, if video is not available). If needed, and at their discretion, the Clinic Operator may join sessions following the Approval too.

A complete session is one which includes at least 40 minutes of stimulation. For each treatment session, after the initiation of the stimulation, a pause in or early cessation of stimulation after the initiation of the stimulation, should be avoided as much as possible. If the stimulation is paused, the session may be reinitiated within 30 minutes. Additional pause before the stimulation is complete (or before 30 minutes of stimulation have been complete in the first 5 occurrences) will result in session termination. If over 30 minutes of stimulation have been completed but the stimulation was stopped before completion, in the first 5 occurrences – the session will be considered complete. Subsequent shortened sessions will be considered incomplete. Missed or incomplete treatment sessions will be rescheduled until 45 treatment sessions are completed. Rescheduled sessions will not result in having over 5 treatment sessions administered in a week. Instead, this will extend the total number of weeks required to complete 45 sessions. Treatment sessions can be completed until the day before the Day 90 follow-up visit. Missed treatments won’t be considered as Protocol Deviation as long as rescheduled and completed within the allowed window (until the day before the 90 Day (± 15) follow up visit).

For treatment schedule disruptions that will lead to subject withdrawal from the study, please refer to § [7.2](#).

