Study Population:	The study will enroll up to 150 adult patients with subacute ischemic stroke, with a moderate to severe disability which includes an upper extremity motor impairment, who will be assigned (1:1 allocation ratio) to either active or sham study intervention using BQ 2.0, initiated 4-21 days after the index stroke event. Following the interim analysis, the sample size may be increased up to 344 subjects. Total enrollment from each site to be no more than 20% of the total sample size.
Study Description:	
The study intervention will be initiated 4-21 days after the index stroke event and will consist of a total of 45 sessions over a period of 9 weeks (5 treatments per week). Each session will last 60 minutes during which 40 consecutive minutes of active or sham study intervention using BQ 2.0 will be administered. Each study group will be guided by the BQ 2.0 application and asked to perform a standardized, pre-defined and evidence-based physical and occupational therapy regimen concurrent with the study intervention. The PT/OT regimen applied in both treatment and sham controlled groups is aligned with the Class 1 level A recommendation for patients with stroke to participate in a home-based rehabilitation program.¹
 
BQ 2.0 does not produce any noticeable sound, light or sensation in connection with the stimulation which may disclose the arm assignment, making it ideal for testing in a sham-controlled setup. During sham treatment sessions, for purposes of maintaining the blind, the device will function as if it is delivering the therapy (i.e., the device will turn on and all indicators will function), but the frequency and intensity parameters that are not visible to the subject or site study members will be set to zero so that no stimulation is delivered.
 
Screening phase
 
Prospective subjects, who are 3 to 21 days post-stroke, will be consented to participate in the study at either:
 
 a) a participating ACH, prior to anticipated transfer to a participating IRF, SNF, outpatient, or home setting; or b) at a participating IRF, SNF, outpatient, or home setting.

¹ Winstein CJ, Stein J, Arena R, et al. Guidelines for Adult Stroke Rehabilitation and Recovery. *Stroke* 2016; 47: e98–e169.

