	
Subjects will undergo a detailed interim outcome assessment on the 20th (± 4) day of treatment, and a detailed primary endpoint outcome assessment on the 90th (± 15) day after the onset of the index stroke. In addition, a focused, long-term outcome assessment on the 180th (± 15) day after the onset of the index stroke will be performed.

Objectives:	
Primary Efficacy To show that the BQ therapy is effective in reducing global disability at 3 months post-stroke in disabled patients with upper limb motor impairment when initiated 4 to 21 days following an ischemic stroke.
 
Secondary Efficacy To show that the BQ therapy is effective in reducing upper and lower limb impairment, and improving upper limb functionality, health-related quality of life (HRQoL), and level of participation in instrumental activities of daily living (ADL) at 3 months post-stroke, when initiated 4 to 21 days following an ischemic stroke.
 
Safety
 
1. To characterize the safety profile of the BQ therapy.2. To show that the BQ 2.0 performs reliably 
Tertiary/Exploratory
 
1. To show that the BQ therapy is effective in reducing cognitive impairment, depression and fine-grained level of disability at 3 months post-stroke, when initiated 4 to 21 days following an ischemic stroke.2. To characterize the long-term effect at 6 months post-stroke of the BQ therapy effect on upper limb functionality and health-related quality of life (HRQoL).3. To formally evaluate the cost-effectiveness of the BQ therapy over a lifetime horizon from the perspective of the United States healthcare system.4. To explore the relationship between adherence to treatment as measured by the Qompass and clinical outcomes
Endpoints:	
Primary efficacy endpoint Modified Rankin Scale (mRS; global disability) change from baseline (4-21 days post-stroke) to 90 days post-stroke.
 
Secondary efficacy endpoints

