1.2 SCHEMA

1.3 SCHEDULE OF ACTIVITIES (SOA)

Procedures	Pre-Screening Phase	Screening, Enrollment & Baseline Visit	Treatments 1-20	Midterm follow-up (in clinic⁵) ± 4 days from 20th treatment)	Treatments 21-45⁶	90 Day Primary outcome assessment (in clinic⁷) 90 Day ± 15 days post-stroke	Additional follow-up (remote) 180 Day ± 15 days post-stroke
Informed consent		X					
modified Rankin Scale (mRS)		X ⁸		X		X	X
Inclusion/exclusion criteria review	X ⁹	X ¹⁰					
Randomization		X					
Investigational/sham device use and intra-session PT/OT			X		X		
Fugl-Meyer Assessment for Upper Extremity (FMA-UE)		X		X		X	
Box and Block Test (BBT)		X		X		X	
Stroke Impact Scale (SIS) Hand Domain		X		X		X	X
Stroke Impact Scale 16 (SIS-16)		X		X		X	
10 Meter Walk Test (10MWT)		X				X	
Shoulder Abduction and Finger Extension (SAFE) score		X					
5-level EQ-5D (EQ-5D-5L)						X	X
Montreal Cognitive Assessment test (MoCA)						X	

⁵ In special circumstances and subject to the approval of the Principal Investigator, visit can be conducted in an outpatient setting or via combined audio and video remote conferencing or audio only, if video is not available.

⁶ Missed or incomplete treatment sessions can be completed up until the day before the 90 Day follow up visit (day 90 ±15).

⁷ In special circumstances and subject to the approval of the Principal Investigator, visit can be conducted in an outpatient setting or via combined audio and video remote conferencing or audio only, if video is not available.

⁸ To be performed after consenting and before all other screening activities.

⁹ Brief review to determine initial eligibility for and interest in the study

¹⁰ mRS and FMA-UE are to be performed again before randomization if more than 24 hours have elapsed since the assessment of the mRS and FMA-UE. If assessments are performed again and subject is eligible, the later scores will serve as the baseline scores and for stratification.

Patient Health Questionnaire-8 (PHQ-8)						X	
Academic Medical Center Linear Disability Scale (ALDS)						X	
Health economics data capture				X		X	X
Demographics	X						
Medical history	X						
Concomitant medications review and evaluation		X	X	X	X	X	X
Vital signs	X			X		X	
Pregnancy test ¹¹	X						
Adverse events review and evaluation		X	X	X	X	X	X
PT/OT done outside of study review			X	X	X	X	
Investigational/sham device use			X		X		
Blinding effectiveness assessment						X	
Device deficiencies review and evaluation			X	X	X	X	

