8.1.1.3 TREATMENTS 1-20

Randomized subjects will undergo the first treatment session no later than 48 hours after randomization and within 4-21 days after stroke onset. Active or sham study intervention sessions using BQ 2.0 (active or sham therapy, respectively) will be conducted 5 times a week, for approximately 9 weeks and until completion of 45 treatment sessions, conducted in either inpatient, outpatient or home setting.

At each of these visits, the subject will undergo a study treatment. Each treatment session will last up to 60 minutes, with active or sham field being turned on for the first 40 minutes. During the session, subjects will be asked to perform a device guided, standardized, pre-defined and evidence-based PT/OT therapy activities, with approximately 30 minutes dedicated to the upper extremity and 30 minutes to the lower extremity, aligned with the Class 1 level A recommendation for patients with stroke to participate in a home-based rehabilitation program.

A trained member of the site study team (the “**Clinic Operator**”) will be responsible for training and approving the subject’s caregiver to operate the session independently.

²⁷ MRI images will be preferred over CT images

	The efficacy of a frequency-tuned electromagnetic field treatment in facilitating the recovery of subacute ischemic stroke patients – a pivotal study		
	No. BQ5	Ver. 4	Page 64 of 150

Before an approval to operate a session independently (the “**Approval**”) is granted by the Clinic Operator, a Clinic Operator will train the caregiver and supervise the sessions, either in-person or remotely. Once an Approval was granted, sessions will be conducted with the assistance of a caregiver while the Clinic Operator will provide periodic oversight (combined audio and video remote conferencing or audio only, if video is not available). If needed, and at their discretion, the Clinic Operator may join sessions following the Approval too.

At each of these visits, the following data will be collected:

- Any changes in concomitant medications
- Any adverse events
- Any device deficiencies
- Duration of stimulation delivered and number of pauses if occurred
- Duration of PT/OT activities performed during the 60-minute period
- PT/OT activities performed outside of study since last visit

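### A late start combined with an early in-window Day 90 visit leaves too little time for 45 sessions before the primary outcome is measured

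*Protocol*

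**What the plan says.** Five statements in the protocol bear on this.

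- **Course.** The synopsis (1.1) and sections 6.1.1 and 6.1.1.5 set 45 sessions at five a week; the synopsis gives this as nine weeks. Section 8.1.1.3 has sessions go on until all 45 are done.
- **Start.** Section 6.1.2 has sessions "starting 4-21 days after stroke onset and no later than 2 days after randomization". Section 8.1.1.3 sets the same limits: "first treatment session no later than 48 hours after randomization and within 4-21 days after stroke onset".
- **Rate.** Section 6.1.2: "Rescheduled sessions will not result in having over 5 treatment sessions administered in a week". Lost sessions lengthen the course: "Instead, this will extend the total number of weeks required to complete 45 sessions".
- **Stop.** Section 6.1.2: "Treatment sessions can be completed until the day before the Day 90 follow-up visit". A footnote to the schedule of activities (1.3) gives the same cut-off.
- **Primary visit.** The synopsis plans "a detailed primary endpoint outcome assessment on the 90th (± 15) day after the onset of the index stroke", which is day 75 to day 105. The schedule of activities uses the same window.

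No section makes the primary visit wait for session 45 or ties its earliest date to the first session.

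**The concern.** The treatment clock starts at the first session and the assessment clock at stroke onset, and the two can be up to 21 days apart. A visit booked at the open end of the window is in order as a visit. For a late starter, though, it can end treatment while sessions are still outstanding.

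Two things are at stake.

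- **The primary contrast.** In such a subject the outcome is read after an incomplete course. It is also read earlier in the roughly three-month period over which section 2.2 expects improvement. Both could make the active and sham arms look more alike.
- **The secondary readings.** Section 9.4.7 lists time from stroke to first treatment as a subgroup, split at about day 14 to 15. It also plans a compliance analysis that relates the number of completed sessions to the primary endpoint. If the number of deliverable sessions depends on start day and visit date, these analyses partly measure scheduling.

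The plan does not remove this. The primary model (9.4.2) adjusts for baseline mRS and age but not for start day, and the per-protocol set (9.3) needs only 20 completed sessions.

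As background only: section 10.4 records the recruitment window widening from days 4–10 to 4–14 and then 4–21. The point rests on the current text.

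**Working it through.** **Inputs** (sections 1.1, 1.3, 6.1.2, 8.1.1.3): 45 sessions; at most 5 per week; first session on day *s*, from 4 to 21; visit on day *V*, from 75 to 105; last treatment day *V* − 1.

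**1. The plan's own figure.** 45 / 5 = 9 weeks, as stated.

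**2. Day of the 45th session, weekdays only, none missed.**
- Monday start: 8 weeks + 4 days = *s* + 60.
- Tuesday to Friday start: 9 weeks − 1 day = *s* + 62.

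A day-4 start therefore ends on day 64–66, and a day-21 start on day 81–83.

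**3. Latest start that allows 45 sessions:** (*V* − 1) − span.

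| Visit day | Monday start | Tuesday–Friday start |
|---|---|---|
| 75 | 74 − 60 = 14 | 74 − 62 = 12 |
| 90 | 89 − 60 = 29 | 89 − 62 = 27 |
| 105 | 104 − 60 = 44 | 104 − 62 = 42 |

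The latest permitted start is day 21. Visits on day 90 or later therefore accommodate every permitted start; a visit on day 75 does not.

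**4. Weekdays available before a day-75 visit.** Days *s* to 74 number 75 − *s*.

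| Start day | Days | Weekdays available |
|---|---|---|
| 4 | 71 = 10 weeks + 1 | 51 |
| 12 | 63 = 9 weeks | 45 |
| 14 | 61 = 8 weeks + 5 | 43–45 |
| 18 | 57 = 8 weeks + 1 | 41 |
| 21 | 54 = 7 weeks + 5 | 38–40 |

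A day-21 start falls 5 to 7 sessions short: 5/45 = 11% to 7/45 = 16%.

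**5. Sensitivity to the schedule.**
- *Weekend sessions, at most 5 per Monday–Sunday week.* The shortest course is a Wednesday start: 5 sessions Wednesday to Sunday, 7 full weeks (35 sessions), then 5 from Monday to Friday. That takes 5 + 49 + 5 = 59 days, a span of 58, so the latest start is 74 − 58 = day 16. Starts on days 17–21 do not fit. A day-21 start still reaches at most 7 × 5 + 5 = 40.
- *One session lost at the midterm visit and not made up* (section 8.1.1.4 allows for this). The span becomes 63, and the latest start is 74 − 63 = day 11.

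**6. Share of the window affected for a day-21 start.** The earliest visit after a full course is day 82 (Monday start) or day 84 (other weekdays). Visits on days 75–81 or 75–83, that is 7 to 9 of the 31 window days, cut the course short even with full attendance.

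**7. Spare room at day 90.** A day-21 start has 69 days (9 weeks + 6), or 49–50 weekdays, so it can miss 4–5. A day-4 start has 86 days (12 weeks + 2), or 61–62 weekdays, so it can miss 16–17.

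**The case against.** The case on the other side has several parts, and most of it stands.

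- **Day 90 is the target and ±15 a tolerance.** Every permitted start fits before day 90, so a reader who infers that the start window flatly contradicts the 45-session course goes too far. Only late start plus early visit conflicts.
- **The protocol leans against that combination.** It reschedules sessions until 45 are done, places sessions 21–45 before the primary visit, and urges early starts. It exempts missed sessions from deviation status only if they are made up before the visit. This stands, but none of it stops an early visit from being booked.
- **A reader might infer that 45 sessions are impossible for any start after day 14.** Section 8.1.1.4 contemplates weekend sessions, and with them a Tuesday start on day 15 or a Wednesday start on day 16 can still finish by day 74. The firm statement applies to days 17–21.
- **A reader might infer that the primary objective goes untested.** Section 3 asks about BQ therapy at three months and does not name a completed 45-session course. The principal efficacy set is everyone who started treatment, analyzed as randomized.
- **A reader might infer bias between arms or an inflated type I error.** The rules are identical in both arms and allocation is blinded, so the documents support neither.
- **The harm is not quantified.** The protocol gives no dose-response data, no recovery slope between days 75 and 90, and no expected share of early visits.
- **Start day and exposure are linked anyway,** because the endpoint is anchored to stroke onset. That is so; the early visit bound strengthens the link.

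**Conclusion.** The point holds in limited form. The window's early end and the later permitted start days do not fit a 45-session course at five a week. The worst case with full attendance is 38–40 of 45 sessions, for a day-21 start and a day-75 visit. The day 12 and day 14 thresholds assume weekday sessions with none missed; the day 17–21 statement also holds with weekend sessions under a Monday–Sunday cap of five.

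The consequence is possible dilution of the treatment contrast, alike in both arms, and some entanglement of exposure with the time-to-first-treatment and compliance analyses. Its size cannot be given, because it depends on how many late starters have early visits. It does not threaten the validity of the primary test. It is worth correcting because the correction is cheap.

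**What to change.** Reconcile the visit window (sections 1.1, 1.3 and 8.1.1.6) with the start window, weekly cap, session total and cut-off (sections 6.1.2 and 8.1.1.3). Whether any treatment rule should change is a clinical matter and is left open here.

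One option, written purely as an assessment rule, is to set the earliest primary visit at the later of day 75 and first session + 63 days, keeping the day-90 target and the day-105 upper bound. Starts up to day 12 see no change (12 + 63 = 75). A day-21 start would be assessed on days 84–105. The bound depends on the start date and not on attendance, so it is the same rule in both arms.

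The text should state three limits:
- It covers only an uninterrupted course. On a weekday schedule the 45th session falls at start + 60 to + 62; one lost session moves it to start + 63, the earliest visit day itself.
- Because treatment stops the day before the visit, the earliest possible cut-off moves with it for late starters.
- Late starters lose up to 84 − 75 = 9 days of early scheduling room, and their assessment window differs from that of early starters.

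The cost is one sentence in section 8.1.1.6, a matching note in the schedule of activities, and a date check in the EDC system.

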6.1.3 CONTROL INTERVENTION DESCRIPTION

Sham intervention is identical to BQ 2.0 therapy, except that no electromagnetic energy is generated by BQ 2.0. Other than that, all provisions of § [6.1.1](#) apply here as well.

6.2 PREPARATION/HANDLING/STORAGE/ACCOUNTABILITY

6.2.1 ACQUISITION AND ACCOUNTABILITY

Investigators will administer study device only to subjects included in this study and following the procedures set out in this protocol. All study devices must be accounted for throughout the study using accountability logs. Investigators must maintain accurate and adequate records, including dates, serial number, quantities received (if applicable), expiry date, inventory, and individual usage. These records will be verified by the study Monitors during site visits.

For information on procedures and particular materials (eg, packaging materials) and instructions for the safe return of investigational devices, including those that are potentially hazardous, please refer to the study MOP.

6.2.2 FORMULATION, APPEARANCE, PACKAGING, AND LABELING

Please refer to the IFU for detailed descriptions.

6.2.2.1 STUDY DEVICE

The BQ 2.0 (active and sham), as provided by the Sponsor for this study, comprises a single package including the *DEVICE*, BQ 2.0, and its accessories, including the *SOFTWARE APPLICATION* installed on an Android-based mobile device and approximately 50 units of the *QOMPASS*, packaged and transported in a custom-made packaging. The packaging is made of fabric and mounted to a wheel system to allow for carrying by hand or wheeling of the device. The packaging includes custom bags and compartment for the BQ 2.0 accessories. Foam padding in the BQ 2.0 packaging maintains the device structure and protects it from damage.

6.2.3 PRODUCT STORAGE AND STABILITY

BQ 2.0 shall be stored in designated packaging in accordance with the requirements specified in the IB.

6.2.4 PREPARATION AND HANDLING

Each BQ 2.0 device will be tested prior to allocation to a study participant.

Upon the completion of all study treatments, in coordination with the site and the study participant, the BQ 2.0 shall be collected and sent to a location designated by the Sponsor or to

the site, for cleaning and refurbishment as described below. A designated Sponsor's representative or study team member will complete the following tasks:

1. Replace all fabrics which can come in contact with an individual to avoid cross contamination
2. Inspect the device thoroughly to ensure all of the components are intact and do not have any visual damage
3. Reset the SW application to allow for a new user to use the application with his/her credentials
4. Test the entire set up by performing a treatment session simulation

For complete product cleaning instructions please refer to the MOP.

Only upon the successful completion of all refurbishment and cleaning tasks shall the device be deemed suitable for reuse on a future study participant.

